4.0 BACKGROUND & RATIONALE

Background

While indolent B-cell non-Hodgkin lymphoma (iNHL) including follicular lymphoma (FL) is not curable with standard therapies, it is highly treatable with chemo-immunotherapy¹⁻³. Retrospective studies have found that up to 80% of FL patients will have overall survival (OS) near age-matched controls, suggesting that many FL patients might have similar outcomes with less intensive therapy^{4,5}. Lenalidomide + rituximab has previously been examined in the upfront setting for 24 months of treatment. While it is “chemo-free,” notable adverse effects include fatigue, cytopenias, and is limited in patients with co-morbidities like chronic kidney disease. Mosunetuzumab, a CD3:CD20 bispecific antibody, and polatuzumab vedotin, an anti-CD79b antibody-drug conjugate, have shown significant activity across multiple B-cell NHL histologies⁶⁻¹⁰. The most recent data of mosunetuzumab monotherapy in relapsed/refractory indolent NHL demonstrated a CR rate of 41%⁶. In addition polatuzumab has been safely combined with obinutuzumab in relapsed/refractory follicular lymphoma with an overall response rate of 78%¹¹.

Obinutuzumab already has an FDA label for treatment-naïve³ and relapsed/refractory¹² follicular lymphoma in combination with chemotherapy. Obinutuzumab has also been used to treat chronic lymphocytic leukemia/small lymphocytic lymphoma in different combinations in the upfront and relapsed refractory settings¹³⁻¹⁵. Obinutuzumab was found to be equivalent to rituximab in aggressive large B-cell lymphomas¹⁵. This makes obinutuzumab an effective partner monoclonal CD20 antibody for treatment of indolent B-cell NHL.

While chemo-immunotherapy is efficacious for untreated iNHL, short-term side effects like fatigue, alopecia, and infections are common, and long-term side effects like secondary malignancies can be seen¹⁶. Given the activity of mosunetuzumab and polatuzumab vedotin in the relapsed/refractory setting, it is reasonable to consider a cytotoxic-chemotherapy-free approach for untreated indolent NHL and expect that CR rates will exceed those seen in the relapsed-setting.

We hypothesize that mosunetuzumab with or without polatuzumab vedotin plus obinutuzumab will produce high complete response rates in indolent non-Hodgkin lymphomas without the need for conventional cytotoxic chemotherapy.

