7.1.6.4 Follow up

After the off study visit, subjects should be followed by their oncologist per institutional standard of care. Study-mandated visits are not required, but the study team may query records to assess disease status or vital status for up to 5 years after completion of therapy. Patients who come off study due to receive alternative therapy should have AEs recorded for up to 30 days after last dose of study treatment or first administration of alternate therapy, whichever comes first.

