The study period during which AEs and SAEs as described within where the patient has been exposed to Genentech product must be reported. Reporting period begins after informed consent is obtained and initiation of study treatment and ends 30 days following the last administration of study treatment or study discontinuation/termination or initiation of alternate anti-lymphoma therapy, whichever is earlier. After this period, investigators should only report SAEs that are attributed to prior study treatment.

Assessment of Adverse Events

All AEs and SAEs whether volunteered by the subject, discovered by study personnel during questioning, or detected through physical examination, laboratory test, or other

means will be reported appropriately. Each reported AE or SAE will be described by its duration (i.e., start and end dates), regulatory seriousness criteria if applicable, suspected relationship to the polatuzumab vedotin (see following guidance), and actions taken.

To ensure consistency of AE and SAE causality assessments, investigators should apply the following general guideline:

Yes

There is a plausible temporal relationship between the onset of the AE and administration of the study drugs (polatuzumab vedotin/ obinutuzumab/ mosunetuzumab), and the AE cannot be readily explained by the subject's clinical state, intercurrent illness, or concomitant therapies; and/or the AE follows a known pattern of response to the polatuzumab vedotin; and/or the AE abates or resolves upon discontinuation of the polatuzumab vedotin, or dose reduction and, if applicable, reappears upon re- challenge.

No

Evidence exists that the AE has an etiology other than the study drugs (polatuzumab vedotin/obinutuzumab/mosunetuzumab) (e.g., preexisting medical condition, underlying disease, intercurrent illness, or concomitant medication); and/or the AE has no plausible temporal relationship to polatuzumab vedotin administration (e.g., cancer diagnosed 2 days after first dose of study drug).

Expected adverse events are those adverse events that are listed or characterized in the Package Insert (P.I) or current Investigator Brochure (I.B).

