- b. Examples of self-care activities of daily living include bathing, dressing and undressing, feeding oneself, using the toilet, and taking medications, as performed by patients who are not bedridden.
- c. If an event is assessed as a "significant medical event," it must be reported as a serious adverse event
- d. Grade 4 and 5 events must be reported as serious adverse events

f. Pregnancy

If a female subject becomes pregnant while receiving the study drug or within 90 days after the last dose of mosunetuzumab or polatuzumab (within 18 months after the last dose of obinutuzumab), or if the female partner of a male study subject becomes pregnant while the study subject is receiving the study drug or within 90 days after the last dose of mosunetuzumab/polatuzumab (or within 180 days after the last dose of obinutuzumab), a report should be completed and expeditiously submitted to Genentech, Inc. Follow-up to obtain the outcome of the pregnancy should also occur. Abortion, whether accidental, therapeutic, or spontaneous, should always be classified as serious, and expeditiously reported as an SAE. Similarly, any congenital anomaly/birth defect in a child born to a female subject exposed to the study drug should be reported as an SAE.

g. Post-Study Adverse Events

The investigator should expeditiously report any SAE occurring after a subject has completed or discontinued study participation if attributed to prior study drug exposure. If the investigator should become aware of the development of cancer or a congenital anomaly in a subsequently conceived offspring of a female subject (including pregnancy occurring in the partner of a male study subject) who participated in the study, this should be reported as an SAE adequately to Genentech drug Safety during follow up period.

h. Case Transmission Verification of Single Case Reports

The Sponsor agrees to conduct the Case Transmission verification to ensure that all single case reports have been adequately received by Genentech via the investigator emailing Genentech a Quarterly line-listing documenting single case reports sent by the investigator to Genentech in the preceding time period.

The periodic line-listing will be exchanged within seven (7) calendar days of the end of the agreed time period. Confirmation of receipt should be received within the time period mutually agreed upon.

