If discrepancies are identified, the Sponsor and Genentech will cooperate in resolving the discrepancies. The responsible individuals for each party shall handle the matter on a case-by-case basis until satisfactory resolution. The sponsor shall receive reconciliation guidance documents within the 'Activation Package'

Following Case Transmission Verification, single case reports which have not been received by Genentech shall be forwarded by the investigator to Genentech within five (5) calendar days from request by Genentech.

At the end of the study, a final cumulative Case Transmission Verification report will be sent to Genentech.

i. AEs of Special Interest (AESIs)

AESIs are a subset of Events to Monitor (EtMs) of scientific and medical concern specific to the product, for which ongoing monitoring and rapid communication by the Investigator to the Sponsor is required. Such an event might require further investigation in order to characterize and understand it. Depending on the nature of the event, rapid communication by the trial Sponsor to other parties (e.g., Regulatory Authorities) may also be warranted.

Adverse events of special interest for this study include the following:

- Cases of potential drug-induced liver injury that include an elevated ALT or AST in combination with either an elevated bilirubin or clinical jaundice, as defined by Hy's law:
 - Treatment-emergent ALT or AST > 3 x ULN in combination with total bilirubin > 2 x ULN

- Treatment-emergent ALT or AST > 3 x ULN in combination with clinical jaundice
- Data related to a suspected transmission of an infectious agent by the study drug (STIAMP), as defined below:
 - Any organism, virus, or infectious particle (e.g., prion protein transmitting transmissible spongiform encephalopathy), pathogenic or non-pathogenic, is considered an infectious agent. A transmission of an infectious agent may be suspected from clinical symptoms or laboratory findings that indicate an infection in a patient exposed to a medicinal product. This term applies only when a contamination of the study drug is suspected.

The polatuzumab vedotin Adverse Events of Special Interest are:

- Neuropathy of Grade 2 or Higher
- Grade 3 or higher infections
- Infusion Associated Reactions
- Hypersensitivity
- Progressive Multifocal Leukoencephalopathy (PML)
- Tumor Lysis Syndrome of any grade (Irrespective of causality)
- Second malignancies

The mosunetuzumab Adverse Events of Special Interest are:

- Grade ≥ 2 CRS

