- Grade ≥ 2 neurologic adverse event
- Any suspected MAS/HLH
- TLS (minimum Grade 3 by definition)
- Febrile neutropenia (minimum Grade 3 by definition)
- Any grade disseminated intravascular coagulation (minimum Grade 2 by definition)
- Grade ≥ 2 AST, ALT, or total bilirubin elevation
- Grade ≥ 2 tumor inflammation/tumor flare, e.g. manifestation of signs/symptoms associated with increase in size of known nodal or extranodal lesions by clinical or radiographic assessment, new onset or worsening of pre-existing pleural effusions

The obinutuzumab Adverse Events of Special Interest are:

- All TLS (irrespective of seriousness, causality or severity)
- Second Malignancies

j. Other Special Situations Reports

The following other Special Situations Reports should be collected even in the absence of an Adverse Event and transmitted to Genentech:

- Data related to the Product usage during breastfeeding
- Data related to overdose, abuse, misuse or medication error (including potentially exposed or intercepted medication errors)
- In addition, reasonable attempts should be made to obtain and submit the age or age group of the patient, in order to be able to identify potential safety signals specific to a particular population

k. Product complaints

A Product Complaint is defined as any written or oral information received from a complainant that alleges deficiencies related to identity, quality, safety, strength, purity, reliability, durability, effectiveness, or performance of a product after it has been released and distributed to the commercial market or clinical trial.

l. Exchange of single case reports

The investigator will be responsible for collecting all protocol-defined Adverse Events (AEs) and Special Situation Reports (including pregnancy reports) originating from the Study for the Product.

Investigators must report all Adverse Events/Serious Adverse events (SAEs), AEs of Special Interest (AESIs), pregnancy reports (occurring in the partner of a male study subject), other Special Situation Reports and Product Complaints with an AE where the patient has been exposed to the product, adequately to Genentech within the timelines described below. The completed MedWatch or Genentech approved reporting forms should be faxed immediately upon completion to Genentech Drug Safety at:

[contact]

Email: [contact]

All Product Complaints without an AE should call via:

PC [contact] (M-F: 5 am to 5 pm PST)

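### Second malignancies are an event of special interest, but systematic all-cause reporting stops about 30 days after the last dose and the record query of up to 5 years does not ask about them

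*Combined protocol and SAP*

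**What the plan says.** Section 7.2.1, item i, names "Second malignancies" among the AESIs for polatuzumab vedotin and "Second Malignancies" among those for obinutuzumab. Both are Part B drugs. The mosunetuzumab list does not include them. Item i asks for ongoing monitoring of AESIs but sets no AESI-specific time window.

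The general window in Section 7.2.1 (Adverse Event Reporting Period) therefore applies. It "ends 30 days following the last administration of study treatment or study discontinuation/termination or initiation of alternate anti-lymphoma therapy, whichever is earlier". The next sentence reads: "After this period, investigators should only report SAEs that are attributed to prior study treatment".

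Item g of the same section (Post-Study Adverse Events) has two relevant sentences. The first keeps the attribution condition: "The investigator should expeditiously report any SAE occurring after a subject has completed or discontinued study participation if attributed to prior study drug exposure". The second begins "If the investigator should become aware of the development of cancer or a congenital anomaly in a subsequently conceived offspring of a female subject" and makes such an event reportable as an SAE during follow-up.

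For long-term follow-up, Section 7.1.6.4 says that "the study team may query records to assess disease status or vital status for up to 5 years after completion of therapy". Section 6.1 footnote 10 and Section 6.2 footnote 6 say the same. New malignancy is not an item.

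Section 4.0, in arguing for a regimen without cytotoxic chemotherapy, says of chemo-immunotherapy that "long-term side effects like secondary malignancies can be seen".

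**The concern.** The plan cites a late harm as part of its motivation, flags it as an event of special interest and allows records to be queried for up to 5 years, but does not ask about that harm in the query. A new cancer well after treatment enters the data only if it is serious and the investigator attributes it to study drug, or if the investigator happens to learn of it and reads item g as covering it.

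Attribution is a weak filter for a late cancer. Several of the causality criteria in Section 7.2.1 are worded around polatuzumab vedotin, which Part A-only subjects never receive. Resolution on stopping the drug and recurrence on re-challenge do not suit a new cancer. Item i waives causality for tumor lysis syndrome under both Part B drugs, but not for second malignancies.

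At stake is the exploratory objective in Section 3.0 of estimating the safety of the regimen by adverse-event frequency. Section 8.0 also says that a promising CR rate is to be weighed with toxicity data, citing the potential for less toxicity.

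**Working it through.** The documents give no ascertainment share and no second-malignancy rate, so there is no planned figure to reproduce. The check compares the length of the all-cause window with the length of possible follow-up.

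**Inputs**
- Cycle length 21 days; last Part A dose on cycle 8 day 1; last Part B dose on cycle 14 day 1 (Section 5.3).
- All-cause reporting to 30 days after last dose (Section 7.2.1).
- Record query up to 5 years after completion of therapy (Section 7.1.6.4), taken as 5 × 365.25 = 1,826.25 days from last dose.
- 42 subjects (Section 8.0).
- Assumed: no dose delays, complete 5-year follow-up, no early discontinuation or alternate therapy.

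**Last dose, counted from first dose**
- Part A only: (8 − 1) × 21 = 147 days.
- Parts A and B: (14 − 1) × 21 = 273 days.

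**Covered share** = (last dose + 30) / (last dose + 1,826.25)

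| | Covered days | Total days | Covered | Uncovered |
|---|---|---|---|---|
| Part A only | 177 | 1,973 | 9.0% | 91.0% |
| Parts A and B | 303 | 2,099 | 14.4% | 85.6% |

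Of the 5-year post-treatment period alone, the uncovered share is 1 − 30/1,826.25 = 98.4% in both groups.

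**Sensitivity to the cut-off.** The flow charts record adverse events up to the off-study visit, 4–6 weeks after last dose, rather than to day 30. With a cut-off anywhere from 28 to 49 days (6 weeks plus a 7-day allowance), the uncovered share is 90.1–91.1% (Part A only) or 84.7–85.7% (Parts A and B). The conclusion does not change.

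**What this could mean in counts.** The documents give no incidence, so a constant 0.5–2% per year is assumed for illustration. Person-years = 42 × days / 365.25; expected events = person-years × rate; chance of no event = exp(−expected).

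| | Person-years, window / full | Expected events, window | Expected events, full | Chance of none, window | Chance of none, full |
|---|---|---|---|---|---|
| All Part A only | 20.4 / 226.9 | 0.10–0.41 | 1.1–4.5 | 67–90% | 1–32% |
| All Parts A and B | 34.8 / 241.4 | 0.17–0.70 | 1.2–4.8 | 50–84% | 1–30% |

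The two rows are extremes; the actual mix of subjects lies between them. At any constant rate, expected events over the full span are 1,973/177 ≈ 11 times (Part A only) or 2,099/303 ≈ 7 times (Parts A and B) those in the window. These ratios concern events that are neither attributed nor picked up through item g.

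**The case against.** The case against rests on five points.

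- **Later cases are not shut out.** Attributed SAEs remain reportable with no end date. The cancer sentence in item g can be read as covering the subject's own cancer, with no attribution condition, and item i calls for ongoing monitoring. This stands in part. A reader might infer that there is no ascertainment after day 30, or that an unattributed late cancer can never be counted; the documents do not support either. They do leave reporting passive and ambiguous, and under the wider reading item g conflicts with the word *only* in the reporting-period text.
- **The attribution rule need not exclude late cancers.** A judgement of unrelated calls for evidence of another cause or an implausible time relation, and the example given is a cancer 2 days after first dose. This is fair, but it leaves the count to case-by-case judgement.
- **The time shares are maxima.** Follow-up is *up to* 5 years and the query is optional. This stands, so the shares hold only if follow-up is complete.
- **A small count is expected anyway.** A reader might infer that the reported frequency will be near zero by construction. That cannot be shown: the documents give no incidence, attributed cases count, and 42 subjects with short exposure would yield few events under any rule. On the assumed rates, none in the window is likely but not certain.
- **No planned analysis depends on it.** Safety is exploratory, with no time horizon, and no second-malignancy frequency or comparison is promised. This stands and limits the weight of the point.

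**Conclusion.** The concern holds as a gap in safety ascertainment. For second malignancies, systematic all-cause reporting covers about 14% of the time from first dose to 5 years after last dose for subjects treated in Parts A and B, the group given the drugs that carry this AESI. It covers about 9% for Part A-only subjects; including them rests on the objective of describing the safety of the whole regimen, not on the AESI list. The complementary 86–91% is a share of treatment plus 5 years. It should not be read as a share of the post-treatment follow-up itself, of which about 98% is uncovered.

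Unattributed late cases would be under-counted in the exploratory safety description. By how much cannot be stated from the documents, because it depends on incidence, attribution, how item g is applied and how complete the query is. The criterion of an observed CR rate of at least 80% is unaffected. The change is worth making because it is cheap, not because the primary conclusion is at risk.

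**What to change.** 1. **Section 7.2.1, reporting period and item i:** state the reporting window for second malignancies. Exempt them from the attribution limit, so that any new malignancy is recorded regardless of causality for as long as the subject is followed. Item i already waives causality for tumor lysis syndrome and offers a model for the wording.
2. **Section 7.2.1, item g:** say explicitly whether the cancer sentence covers the subject's own cancer, and make it agree with the reporting-period text.
3. **Section 7.1.6.4, Section 6.1 footnote 10 and Section 6.2 footnote 6:** add new malignancy to the record query for disease and vital status, for all treated subjects including those who receive Part A only.
4. **Section 8.0:** report the number of second malignancies with time at risk to last query, separately for Part A-only and Part A plus B subjects.

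The cost is one more item in a query the plan already provides for, in 42 subjects, plus the wording changes. The downside is slightly more data abstraction and possibly a less favourable count.

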8.0 STATISTICAL ANALYSIS PLAN: STUDY DESIGN AND STATISTICAL ANALYSIS PLAN

Mosunetuzumab has been extensively studied as monotherapy in the relapsed refractory setting⁶. However, we will have the following safety suspension parameters.

First, any on-treatment death will prompt a suspension of accrual and convention of an ad-hoc safety committee may recommend changes to the protocol and its analysis based on updated information, closure of the protocol, or continued accrual with no modifications.

In addition, we would expect that grade 4 non-hematologic toxicity will be uncommon (< 10%) and is uncommon in standard chemoimmunotherapy. We will suspend accrual until an ad hoc safety committee can be convened to review the event and make recommendations regarding protocol modification or closure if the following criteria are met: If the lower limit of a 95% confidence interval does not include the possibility of this rate being < 10%. Operationally, this would mean if $\geq 5/15$, $\geq 7/30$ or $\geq 9/42$ patients have a grade 4 non-hematologic treatment-related toxicity (excluding CRS as this is evaluated separately).

Grade 2+ CRS is uncommon as well in the relapsed/refractory⁶ as well as untreated setting²¹ and would expect this rate to be < 15%. We will suspend accrual until an ad hoc safety committee can be convened to review the event and make recommendations regarding protocol modification or closure if the following criteria are met: If the lower limit of a 95% confidence interval does not include the possibility of this rate being < 15%. Operationally, this would mean if $\geq 6/15$, $\geq 9/30$ or $11/42$ patients have a grade 2 or higher CRS event.

In addition, this protocol will be monitored by the institutional data safety monitoring committee at regular intervals.

As mosunetuzumab has been extensively studied as monotherapy in the relapsed refractory setting, and obinutuzumab and polatuzumab in combination were not associated with any significant safety concerns (for example, anti-CD20 antibodies can safely be combined with polatuzumab and combination chemotherapy for an equivalent length of time⁷), no specific safety stopping rules will be established. However, this protocol will be monitored by the institutional data safety monitoring committee at regular intervals.

Objectives include gaining a preliminary assessment of the potential efficacy of this regimen. This will be defined as the percentage of patients that achieve a complete remission (CR) following study treatment as the primary end point, best ORR as a secondary end point. Exploratory endpoints include with PFS and OS. A simple binary proportion will be used to estimate CR and ORR, and the Kaplan-Meier method will be used to estimate PFS and OS.

Combination chemotherapy with a CD20 monoclonal antibody is highly efficacious in the treatment of indolent lymphomas, but short and long term toxicities can be seen¹⁻³. Since these studies did not all use PET-based assessments, it can be challenging to determine a reasonable

benchmark. However, recent retrospective studies would suggest the CR rate to upfront treatment is around 80%²⁵. Given potential for less toxicity with the proposed treatment, an observed CR rate that is at least as high as this benchmark would be considered promising, pending examination of other endpoints plus toxicity data. Therefore we would consider this study to be successful and merit further investigation if the observed best response as CR rate that is at least 80% among the patients treated. We propose to treat a total of 42 patients, this number not based on considerations of statistical power to reject a null hypothesis, rather on considerations of feasibility and ability to accrue. We anticipate enrolling roughly 42 patients over a 30-month period, but if the protocol is open for 36 months before 42 patients have been enrolled, consideration will be given to closing the study. If we enroll 42 patients, 34 or more complete responses would meet this benchmark. Shown in the table below is the probability of 34 or more responses among 42 patients for a variety of assumed-true CR rates. A subject will be defined as efficacy evaluable if they have had at least one response assessment. Subjects who come off study treatment for any reason prior to a response assessment will not be considered response evaluable and will not be replaced. If fewer than 42 subjects are evaluable for response after completion of the study, we will recalculate the below tables with a goal of achieving a CR as best response in at least 80% of patients.

Assumed-true CR rate	Probability of 34 or more responses among 42 patients
.65	.02
.70	.08
.75	.24
.80	.53
.85	.83
.90	.98

Shown in the table below are the lower one-sided 80% and 90% confidence limits for a variety of observed response rates among 42 patients.

Observed response proportion	Point estimate	Lower one-sided 80%, 90% confidence limit
27/42	64%	57%, 53%
31/42	74%	66%, 63%
36/42	86%	79%, 76%
38/42	90%	85%, 82%

We also propose interim efficacy evaluations with suspension rules. Primary progressive disease with rituximab monotherapy²⁶ and rituximab + chemotherapy¹ is rare, with most cases likely due to occult transformation. If 2 out of the first 20 (or fewer) subjects have primary progressive disease (an observed rate of 10% or higher), the study will be suspended to enrollment pending the recommendations of an ad-hoc safety committee. The lower one-sided 80% confidence limit for 2/20 is 4%, and therefore with such an occurrence (or among fewer than 20 patients) we'd be reasonably confident that the true rate is greater than 4%. Since progressive disease in this population has been rare, this rule is relatively strict. Patients who

have suspected or biopsy-proven transformed disease will not count as an event for the purposes of this analysis. Since pseudo-progression can be seen with immunotherapy drugs like mosunetuzumab, subjects with overall reduced tumor burden that meet criteria for progression due to discordant response among tumor sites will also not count as an event for the purposes of this analysis.

We also acknowledge that chemo-immunotherapy is associated with high overall response rates of around 90%¹, and we propose an interim analysis with a suspension rule for lack of sufficient efficacy. If 14 or fewer of the first 20 subjects do not achieve an objective response of PR or CR as best response by the end of study treatment (an observed rate of 70% or less), the study will be suspended to enrollment pending the recommendations of an ad-hoc safety committee. The upper one-sided 80% confidence limit for 14/20 is 79%, and therefore with such an occurrence we'd be reasonably confident that the true response rate is less than 80%, the loose benchmark that we are using to define success for this trial.

In both cases, the ad-hoc safety committee may recommend changes to the protocol and its analysis based on updated information, closure of the protocol, or continued accrual with no modifications.

